3.1.4 TREATMENT PHASE

For the purpose of the trial, all participants will be asked to use their allocated study device for two 30-minute sessions per day, a minimum of five hours per week for 12 weeks at suprathreshold (twice the individual motor threshold or as much as the participant can tolerate as comfortable). If participants do not perceive any sensation or muscle contractions, they should be encouraged to use their study device at the highest stimulation intensity (level 99), provided there are no other concerns with using the device at this level. The maximum total treatment time of 3 hours per day will be advised to minimise the potential for muscle fatigue. Adherence to treatment will be recorded in a patient diary and collected via the Revitive App. Participants will also receive

Research Governance and Integrity Team

reminders to complete their treatment sessions via the Revitive App. Study smartphones will be provided for participants to access the Revitive App.

3.1.5 STUDY DEVICE ACCOUNTABILITY

During the clinical trial, the study devices will be fully traceable due to individually assigned device codes. Access to study devices will be restricted to authorised persons only and appropriate records will be kept by the device manufacturer, study coordination centre and clinical trials sites to document the physical location of all study devices from shipment from the device manufacturer to the clinical trial sites, provided to participants for the clinical trial period (12 weeks), returned to the clinical trial site and then provided to participants to keep at the end of the trial. Records will be kept of who received, used, returned or disposed (if applicable) of the study devices.

3.2 RANDOMISATION STRATEGY

Participants will be randomised in a 1:1 design, intervention: control at baseline to the following groups:

- 1. Sham Device + Standard of Care (Control group)
- 2. NMES Device + Standard of care (Intervention group)

The online computer software application Sealed Envelope (London, UK) will be used for randomisation, and it will be programmed with a randomisation schedule blocked with random block sizes. To ensure concealment, the block sizes will not be revealed until the analysis stage (after last patient last visit).

Randomisation and study assessments must be performed by a blinded researcher. The blinded researcher will confirm the eligibility criteria that must be met to allow randomisation on the online service. Once confirmed, Sealed Envelope will provide a study device code rather than treatment allocation. The unblinded randomisation list 'code-break' for treatment allocation will remain concealed from the study team and be held by the device manufacturer and an unblinded researcher at the study coordination centre who will not interact with participants.

There will be no randomisation within sites because 'there are only two clinical trial sites planned, with the majority of recruitment expected to take place at Imperial College Healthcare NHS Trust. This is also consistent with Food and Drug Administration (FDA) Good Review Practice guidance, which suggests that stratification by centre is not feasible for multi-centre trials with small numbers recruited per site (28).

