3.1.1 STANDARD OF CARE

Standard of care is defined as the therapy for DN available locally to the clinical trial site. It can comprise of advice on glycaemic control, footcare, anticonvulsant and antidepressant medications. For pragmatism, standard of care will be as per local guidelines and is not standardised by the study protocol. A full medical and drug history will be taken at baseline and concomitant medications will be recorded and monitored at each study visit. There are no prohibited concomitant medications for this trial.

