- Nerve conduction study (NCS) (central site only) The sural, common peroneal, tibial and superficial peroneal nerves will be bilaterally tested. All NCSs will be performed by a single, blinded researcher (a highly trained neurophysiologist) at the core lab at Imperial College Healthcare NHS Trust to reduce inter-operator variability. A separate Nerve Conduction Study (NCS) Protocol will outline how NCSs for this trial are conducted. If a NCS has been performed within 3 months of consent by the blinded researcher (a highly trained neurophysiologist) as part of standard of care, this NCS can be used instead, and it does not need to be repeated as part of the baseline visit.
- Quantitative Sensory Testing (QST) (central site only) Somatosensory nerve fibre function will be assessed using the German Research Network on Neuropathic Pain (DFNS) QST protocol (29).

Research Governance and Integrity Team

The battery of tests includes measures of cold and warm detection thresholds, paradoxical heat sensations, cold and heat pain thresholds, mechanical detection threshold, mechanical pain threshold, mechanical pain sensitivity, dynamic mechanical allodynia, temporal pain summation, vibration detection threshold and pressure pain threshold. Testing will take place on the worst affected limb.

- Berg Balance Scale (BBS) Mobility and balance will be assessed using the validated measure (25).
- Neuropathic Pain Symptom Inventory (NPSI) Neuropathic pain will be assessed using the validated measure (26).
- Total Symptom Score (TSS) Symptoms (paraesthesia, pain, numbness, cramp and sleep disruption) will be assessed on a 10-point Numerical Rating Scale (NRS) and scores will be combined to give a TSS out of 50.
- Monofilament test Protected sensation will be objectively assessed using a monofilament test. A 10g monofilament will be perpendicularly applied to five sites (1st, 3rd, and 5th metatarsal heads and plantar surface of the hallux and 3rd toe) of both feet for approximately two seconds each to cause the filament to bend. The participant will be asked if they felt the pressure applied or not at each site.
- Patient diary Clinical trial site staff will provide a patient diary to
 participants to collect daily device usage for the 12-week treatment
 phase (i.e. adherence to treatment). Timed used and intensity level
 setting will be recorded. Although device usage will be collected via the
 Revitive App, a diary will also be provided to verify the Revitive App

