8. STATISTICAL ANALYSES

8.1 SAMPLE SIZE CONSIDERATIONS

The target sample size is 64 participants (32 participants per group), which includes an expected 10% loss to follow up rate at 6 months. Therefore, the final number of participants with primary outcome measure data is expected to be 57.

As the previous research in this area has been limited, and the treatment effect of NMES on DN is unclear, a sample size could not be determined using a power calculation. A previous proof-of-concept study found a mean reduction of 1.75 points in the total score of the MNSI Part A questionnaire after 10 weeks of NMES therapy (22). For the defined objectives, the chosen target is realistic to achieve in this clinical setting and provide sufficient pilot data to assess the potential efficacy signal, feasibility and safety of a NMES device. This study will serve as the foundation for future powered RCTs investigating NMES in DN.

Further details on sample size and minimal clinically important difference considerations will be included in the **Statistical Analysis Plan (SAP)**, authored by members of the statistical support team and agreed by the Trial Management Group (TMG). The **SAP** will be finalised prior to database lock.

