8.2.1 PRIMARY OUTCOME MEASURE ANALYSIS

The primary outcome measure is the MNSI Part A questionnaire total score, which measures neuropathy symptoms using at 12 weeks. The difference in change in the MNSI Part A questionnaire total score, between the two treatment groups at 6 weeks, 12 weeks and 26 weeks will be analysed using Analysis of Covariance (ANCOVA) models. The primary timepoint of interest is at 12 weeks, but neuropathy symptoms at 6 weeks and 26 weeks will also be evaluated. Each model will include a term for treatment and baseline MNSI Part A questionnaire total score as a covariate. The ANCOVA will be applied to each of the multiply imputed datasets and then combined using Rubin's method. If the assumptions underlying the ANCOVA are violated, alternative non-parametric methods, such as a rank ANCOVA will be considered. A p value of ≤ 0.05 is to be considered significant. Full details of the multiple imputation process will be provided in the **SAP**.

Imperial College Healthcare

Research Governance and Integrity Team

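### Site is left out of the randomisation and of the fixed primary ANCOVA on a rationale that does not fit two sites; the analysis stays valid, but one pre-specified site term would be a cheap gain

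*Protocol*

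**What the plan says.** Protocol section 3.2 plans 1:1 randomisation from one list with random block sizes and no stratification factor. It gives two reasons for leaving site out. Only two sites are planned, with most recruitment at the central one. And this is said to agree with guidance that "stratification by centre is not feasible for multi-centre trials with small numbers recruited per site".

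Section 8.2.1 states the covariates of the primary analysis: "Each model will include a term for treatment and baseline MNSI Part A questionnaire total score as a covariate". It sends the details of the multiple imputation to the SAP. Section 8.2 sends further analysis detail there in general terms.

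On differences between sites, section 3.1.1 says that "standard of care will be as per local guidelines and is not standardised by the study protocol", and that care may include anticonvulsant and antidepressant drugs. Section 5.4 has nerve conduction done "by a single, blinded researcher (a highly trained neurophysiologist) at the core lab at Imperial College Healthcare NHS Trust to reduce inter-operator variability". It makes no such provision for the other assessments.

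On size, section 8.1 says: "The target sample size is 64 participants (32 participants per group), which includes an expected 10% loss to follow up rate at 6 months", and "the final number of participants with primary outcome measure data is expected to be 57". It adds that "a sample size could not be determined using a power calculation".

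**The concern.** The reason given in section 3.2 does not match the design. Guidance about small numbers per site, as the protocol paraphrases it, addresses trials with many thin strata. Two strata, one holding most of 64 participants, is close to the easiest case for stratification. That there are only two sites argues for feasibility rather than against it.

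A trial that does not stratify by site can still adjust for it. Section 8.2.1 closes that route for the primary outcome by naming the model terms. The protocol itself supplies a reason why site could matter there: background treatment for neuropathy is local, and that treatment can affect symptoms.

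With one list across both sites, the arms can by chance hold different shares of second-site participants. If the sites differ in 12-week MNSI Part A given baseline, that imbalance moves the treatment estimate in this one trial, and the site difference stays in the residual variance. A site term deals with both. Site is known for every participant, and the result will inform the decision on a powered trial.

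**Working it through.** **The protocol's own figure.** 64 x (1 - 0.10) = 57.6, which rounds down to the 57 stated in section 8.1. The protocol gives no power, effect size or SD, so there is no power figure to reproduce.

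**Inputs.** N = 57 evaluable (section 8.1) and 1:1 allocation (section 3.2). *Assumed*, because the protocol gives no value: second-site share p from 10% to 40%, and a site difference d of 0, 0.5 or 1.0 residual SD, where the residual SD is that of the ANCOVA given baseline.

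**Chance imbalance.** The SD of the between-arm difference in second-site share is sqrt(4p(1-p)/N). With N = 57:

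| p | SD of difference |
|---|---|
| 10% | sqrt(4 x 0.09/57) = 0.079 |
| 20% | sqrt(4 x 0.16/57) = 0.106 |
| 30% | sqrt(4 x 0.21/57) = 0.121 |
| 40% | sqrt(4 x 0.24/57) = 0.130 |

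In simulation (58 evaluable, assumed blocks of 2, 4 and 6) the 95th percentile of the absolute difference was about 14, 21, 24 and 24 percentage points. Multiplied by the site difference, the 95th-percentile shift in the estimate is 0.07 to 0.12 SD when sites differ by 0.5 SD, and 0.14 to 0.24 SD when they differ by 1.0 SD.

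The probability of exceeding a fixed threshold is a poor summary here because it turns on odd versus even counts. For an arm difference of at least 12.5 points among 64 randomised, it is 34%, 21% and 36% with 12, 13 and 14 second-site participants.

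**Precision.** Leaving site out adds about p(1-p)d² to a residual variance of 1. Putting it in costs about (N-4)/(N-5) = 53/52 = 1.019. The variance ratio, with site over without, is therefore about 1.019 / (1 + p(1-p)d²):

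| p | d = 0 | d = 0.5 | d = 1.0 |
|---|---|---|---|
| 10% | 1.02 | 1.019/1.0225 = 1.00 | 1.019/1.09 = 0.93 |
| 20% | 1.02 | 1.019/1.04 = 0.98 | 1.019/1.16 = 0.88 |
| 30% | 1.02 | 1.019/1.0525 = 0.97 | 1.019/1.21 = 0.84 |
| 40% | 1.02 | 1.019/1.06 = 0.96 | 1.019/1.24 = 0.82 |

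Simulation of the ANCOVA with and without site agrees to within about 0.01 to 0.02. Break-even is at d = sqrt(0.019/(p(1-p))): about 0.46 at 10%, 0.34 at 20% and 0.28 at 40%.

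**Validity and power.** A second simulation used 58 evaluable, an assumed baseline correlation of 0.5, an assumed treatment effect of 0 or 0.67, and effects in outcome SDs within site (1.0 of these is 1/sqrt(0.75) = 1.15 residual SDs). The mean estimate was unbiased in every scenario. Type I error was 4.5% to 5.6% with or without site, which is simulation noise around 5%. Power at the assumed effect of 0.67, without and then with site:

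| p | site effect 0.5 SD | site effect 1.0 SD |
|---|---|---|
| 10% | 82% to 82% | 77% to 82% |
| 20% | 80% to 81% | 74% to 82% |
| 30% | 80% to 81% | 72% to 81% |
| 40% | 78% to 80% | 69% to 80% |

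At 0.25 SD there was no material gain.

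**The case against.** The strongest reply is that nothing here is invalid. Randomisation was not stratified, so an ANCOVA without site matches the design. Its standard error already allows for chance imbalance in site, as it does for diabetes type or HbA1c. This stands. A reader might infer bias or an inflated type I error, and the check shows neither.

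The gain also rests on two quantities that the protocol does not give. Below roughly 0.3 to 0.5 residual SD the site term gains nothing or costs slightly, and a 1.0 SD site difference is large and unsupported by any passage. For a pilot without a power calculation this limits the severity. That stands too.

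It may be said that the second site could be small enough for the guidance to fit. It could, for that one stratum; the other would still hold most participants. Whether the guidance itself says more cannot be judged from the protocol.

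Two stronger readings are tempting and not supported:

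- **Raters.** A reader might conclude that different assessors at the two sites distort the primary comparison. MNSI Part A is a yes/no questionnaire answered by the patient (section 2.3). The single-operator sentence concerns nerve conduction, which is done at the central site only. Different raters by site for MNSI Part B, Berg Balance and monofilament is an inference. Section 3.4 requires trained staff, and a constant rater offset would largely cancel in change from baseline.
- **Secondary outcomes.** A reader might conclude that site is also omitted there. Section 8.2.4 leaves the adjustments open, and the SAP, which is not available here, may include site.

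**Conclusion.** The point holds as a minor one. The rationale in section 3.2 does not fit a two-site trial with most participants at one site. Section 8.2.1 then fixes a primary model without site, so a fully observed factor that could plausibly matter through local care is controlled nowhere for the primary outcome.

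The cost is precision and a possible chance shift in this one allocation. For 57 evaluable participants and an assumed second-site share of 10% to 40%, a site term changes the variance of the treatment estimate by about +1% to +2% if the sites do not differ, by 0 to -4% at a difference of 0.5 residual SD, and by -6% to -18% at 1.0. Which of these applies cannot be settled from the protocol. The case for acting is the asymmetry between a small known cost and a possible moderate gain, together with the need to choose the covariate before the data are unblinded.

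**What to change.** Before unblinding:

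1. In section 8.2.1 and the SAP, add site (two levels) as a fixed effect to the primary ANCOVA, and carry it into the imputation model so that the two agree.
2. Leave the randomisation list unchanged.
3. In section 3.2, remove the small-numbers rationale. State simply that randomisation is not stratified by site and that site is adjusted for in the analysis.
4. As a suggestion for consistency, not a correction, use the same term for secondary outcomes collected at both sites: TSS, NPSI, MNSI Part B, Berg Balance, monofilament and HbA1c. Nerve conduction and QST are done at the central site only and need none.

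The cost is a sentence or two of text, one degree of freedom, and up to about 2% more variance if the sites turn out not to differ.

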3.3 BLINDING PROCESS

As this is a double-blind study, both participants and researchers (including

Imperial College Healthcare

Research Governance and Integrity Team

outcome assessors) will be blinded to treatment allocation. Participants will be aware it is a double-blind study, in that there is a 50% chance they will be randomised to a sham device. At the study coordination centre, there will be an unblinded researcher who will not interact with patients. The unblinded randomisation list 'code-break' will only be accessible to the device manufacturer and unblinded researcher.

Participants may not perceive any sensation or muscle contractions because the sham device produces very low stimulation and/or because of their diabetic neuropathy (a disease characterised by sensorimotor dysfunction). Participants in the active NMES arm may also not perceive any sensation or muscle contractions because of their diabetic neuropathy.

During the course of a trial, unblinding should only occur if it is relevant to the safety and medical management of the participant. The final decision of unblinding will rest with the treating clinician. Ideally, where time allows, there should be a discussion with the Chief Investigator (CI) about the need to unblind; if this is not an option, the PI should notify the CI as soon as possible afterwards. The unblinded researcher at the study coordination centre will only share the treatment allocation details of the participant required to be unblinded, the full unblinded randomisation list 'code-break' will still be concealed from the study team. Every effort should be made to limit sharing treatment allocation details to the treating clinician and not to divulge this to the study team, PI (unless treating clinician) and CI.

All requests for unblinding should be documented including details of who made the request, who performed it, how it was carried out and the reason. The treatment allocation should not be included on this documentation as it could unblind further members of the clinical trial site team. The local PI is responsible for ensuring that the documentation is completed, a copy is filed in the Investigator Site File, and a copy is sent to the Trial Manager/Monitor for filing in the TMF. A record should also be made in the participant's medical notes, case report form (CRF) and electronic Case Report Form (eCRF) to document the unblinding.

3.4 STUDY SETTING

This study is open to all patients at the participating NHS sites (Table 2) meeting specific inclusion and exclusion criteria.

Research Governance and Integrity Team

Table 2: Clinical trial sites

Number	Principal	Address	Institution	Country
	Investigator			
1.	[name] Cross	Imperial	UK
	[name]	Hospital	College	
		Fulham Palace	Healthcare	
		Road	NHS Trust	
		[name]		
2.	[name]	Basildon and	Mid and	UK
		Thurrock	South Essex	
		University	NHS	
		Hospital	Foundation	
		[name]	Trust	

These clinical trial sites have been selected because the local PIs have indicated the trial is feasible and that they have the capacity and capability to conduct the trial at their site. In addition to clinical trial sites, potential participants will also be identified from community settings who will act as participant identification centres (PICs). These PICs will conduct a search of the patient record database and suitable participants will be contacted either via letter, mailout or text to inform them about the study. Interested patients would contact the clinical trial site team directly for more information.

All delegated clinical trial site staff must be appropriately trained in order to carry out the study assessments and procedures, and this must be approved by the study coordination centre at Imperial College London who will provide the "green light" for participant recruitment once training has taken place and appropriate regulatory approvals have been received. The majority of training will be completed at the Site Initiation Visit (SIV). In particular, there will be training on data collection, responding to data queries and general information on obtaining high-quality research data.

3.5 LENGTH OF STUDY

The duration of the study is 22 months: 16 months recruitment and 6 months follow up (end of treatment phase is at 3 months; end of follow up is at 6 months). Recruitment started on 22 August 2023.

4. SELECTION AND WITHDRAWAL OF PARTICIPANTS

4.1 DIAGNOSTIC CRITERIA

4.1.1 DIABETES DIAGNOSTIC CRITERIA

A confirmed diagnosis of diabetes, either type 1 or type 2.

Research Governance and Integrity Team

4.1.2 DIABETIC NEUROPATHY DIAGNOSTIC CRITERIA

For the purposes of the trial, a diagnosis of DN will be based on a validated screening questionnaire for DN using the Michigan Neuropathy Screening Instrument (MNSI) – a questionnaire score of \geq 4, which is considered abnormal, and more sensitive and specific than the previously defined cut-off point of \geq 7 (23,24)

4.1.3 NEUROPATHY SCREENING

Other causes of peripheral neuropathy will be excluded by taking a medical history.

The following blood tests will be collected and processed locally:

- a. Folate
- b. Vitamin B12
- c. Thyroid function
- d. HIV (optional)

Any abnormalities in blood test results will be recorded, patients will be excluded from the trial and receive appropriate written information. The patient's General Practitioner (GP) will be informed with the consent of the patient.

An additional HbA1c blood test will be collected at screening and Week 12, but this is not part of neuropathy screening.

4.2 INCLUSION CRITERIA

- Aged ≥18 (no upper limit)
- Diagnosis of type 1 or type 2 diabetes based on World Health Organisation (WHO) definition Diagnosis of diabetic neuropathy based on the validated screening questionnaire Michigan Neuropathy Screening Instrument score of ≥4
- Access to internet at home to use the Revitive App (study smartphones will be provided)

4.3 EXCLUSION CRITERIA

- Lacks capacity to provide informed consent
- Pregnant
- Implanted electronic, cardiac or defibrillator device
- Other cause of peripheral neuropathy
- Current foot ulceration
- Severe vascular disease requiring invasive intervention
- Being treated for, or have the symptoms of, an existing deep vein thrombosis (DVT)

Imperial College Healthcare

Research Governance and Integrity Team

 Regularly used a neuromuscular electrical stimulation (NMES) device within 1 year of randomisation

